STUDY PROTOCOL

June 23, 2016

NCT03365011

NITROUS OXIDE AS TREATMENT FOR TINNITUS – A PILOT STUDY

Principal Investigator:

[name], FACS, CPI

Professor of Otolaryngology, Director of Clinical Outcomes Research

Department of Otolaryngology - Head and Neck Surgery

Washington University School of Medicine

[contact] (office)

[contact]

Sub-Investigators:

[name], MSc

Associate Professor of Anesthesiology and Genetics

Department of Anesthesiology

Washington University School of Medicine

[contact]

[contact]

[name]

Department of Psychiatry, Professor of Psychiatry, Director of Treatment Resistant Depression and Neurostimulation Clinic

[name], MPH, Biostatistician, Department of Otolaryngology - Head and Neck Surgery, Washington University School of Medicine

[name], Medical Student (MD Candidate), Washington University School of Medicine

Study Title	Nitrous oxide as treatment for tinnitus – a pilot study
Objective	This pilot study aims to determine if nitrous oxide (laughing gas) is efficacious as treatment for subjective tinnitus.
Study Period	Planned enrollment duration: Approximately 6 months. Planned study duration: 1 year
Number of Patients	40
Study Drug	Nitrous oxide (laughing gas). This is an FDA-approved general anesthetic and sedative agent used in hospitals and dentist offices. The use of nitrous oxide to treat tinnitus is off-label and outside of the approved indication. Nitrous oxide will be administered under supervision of an attending-level anesthesiologist and using standard anesthesia equipment (mobile anesthesia machine, standard peri-procedural monitoring, oxygen, rescue equipment).
Study Design	Prospective, randomized, double-blinded, placebo-controlled cross-over trial. Subjects will first receive either up to 50% nitrous oxide/50% oxygen or “placebo” (50% nitrogen [inert]/50% oxygen) in a 40-minute single session. In the subsequent session, subjects will receive the other treatment intervention. The two sessions will be held 2 weeks apart and will be indistinguishable from each other in setting, setup, and monitoring.
Inclusion and Exclusion Criteria	
Inclusion Criteria
 
 a) Adult men and women 18-65 years of age b) Subjective, unilateral or bilateral, non-pulsatile tinnitus for at least 6 months duration c) Either “Bothered more than a little but not a lot”, “Bothered a lot”, or “Extremely bothered” on the Global Bothersome scale d) Able to give informed consent e) Must be able to read, write, and understand English 
Exclusion Criteria
 
History of:
 
 a) Bipolar disorder b) Schizophrenia c) Schizoaffective disorder d) Substance abuse or dependence (except for remote substance abuse or dependence with remission at least 1 year prior to the study and except for nicotine use disorders) e) Acute medical illness that may pose subject at risk during nitrous oxide administration f) Active psychotic symptoms g) Patients with significant pulmonary disease and/or requiring supplemental oxygen h) Contraindication against the use of nitrous oxide: 
 a. Pneumothorax b. Bowel obstruction c. Middle ear occlusion d. Elevated intracranial pressure e. Chronic cobalamin and/or folate deficiency treated with folic acid or vitamin B12 f. Pregnant patients g. Breastfeeding women i) Previous administration of NMDA-receptor antagonists (e.g., ketamine) within the last 3 months j) Tinnitus related to cochlear implantation, retrocochlear lesion, Meniere’s Disease, or other known anatomic lesions of the ear or temporal bone k) Tinnitus related to a Workman’s Compensation claim or litigation-related event that is still pending. l) Any medical condition, which, in the opinion of the PI, confounds study results or places the subject at greater risk
Primary Outcome and Measurements	The difference in the difference in patient-reported tinnitus symptoms according to Tinnitus Functional Index (TFI) between baseline and 1 week after each intervention. Secondary outcome measure will be the same calculation performed for the Momentary Assessment of Tinnitus (MAT) questionnaire.

ABSTRACT

Tinnitus, the perception of sound in the absence of external acoustic stimulation, is a common yet poorly understood disease that currently lacks effective front-line treatment. Many therapies focus on mitigating the effects of tinnitus on patients' quality of life, such as through habituation or masking with white noise. However, the tinnitus research literature suggests that NMDA receptor antagonists may prove to be useful in reducing tinnitus itself.[6, 9, 11, 12] Nitrous oxide belongs to the class of NMDA receptor antagonists, and additionally is widely-used, non-invasive, and has a proven safety profile. As such, nitrous oxide may be the drug of choice for testing the efficacy of NMDA receptor antagonists on reducing subjective, bothersome tinnitus.

We propose conducting a pilot randomized placebo-controlled, double-blind crossover study in which patients attend two sessions where they receive either 50% nitrous oxide in oxygen or 50% nitrogen, 50% oxygen for a period of 40 minutes. Tinnitus will be assessed using the Tinnitus Functional Index (TFI) upon enrollment, then reassessed 1 week following each intervention session. Secondly, the Momentary Assessment of Tinnitus (MAT) questionnaire will be administered at baseline before intervention, 1 hour after intervention, 1 day after intervention, and 1 week after intervention.

1. SPECIFIC AIMS

Aim 1. To evaluate the efficacy of nitrous oxide as treatment for tinnitus

2. BACKGROUND

Subjective, idiopathic, non-pulsatile tinnitus ("tinnitus") is perception of sound without the presence of an external acoustic stimulus. Approximately, 60 million Americans experience chronic tinnitus and 15 million of these people have bothersome tinnitus. Research at Washington University (WU)[1] and elsewhere showed that bothersome tinnitus is associated with poorer working memory, slower processing speeds and reaction times, and deficiencies in selective attention. These findings indicate that tinnitus interferes with attention and other important non-auditory cortical networks and the effects may be mediated by stress and its

effects on the central nervous system.

Currently, no effective front-line therapy exists for tinnitus. Many patients use external sound therapy such as white noise generators to mask the perceived sound, or counseling therapy to habituate the patient to the perceived sound. While these treatments often help decrease the effects tinnitus has on quality of life, they do not alleviate the tinnitus itself. Surgical treatment such as nerve transection remains controversial.[2, 3] Currently, there are no FDA-approved drugs specifically for tinnitus.[4, 5, 6] However, there are antidepressant and anti-anxiety medications such as desipramine (Norpramin), alprazolam (Xanax), or lorazepam (Ativan) prescribed to patients with tinnitus.[6, 7] According to the American Tinnitus Association, these psychotropic drugs can reduce the psychological burden of tinnitus for some patients, but again do not reduce perception of tinnitus itself. Furthermore, side effects of the drugs include nausea, blurred vision, and insomnia, and they can be habit-forming. As such, the side effects often interfere with patients' ability to concentrate and with other cognitive functions.[7]

A previous trial performed by [name] at WU examined using nitrous oxide as a treatment for major depressive disorder (MDD). Results showed significant and rapid improvement of depressive symptoms.[8] Nitrous oxide is an N-methyl-D-aspartate (NMDA) receptor antagonist, a class of drugs that have shown to have antidepressant effects.[9] There is a general consensus in tinnitus research that subjective neural-generated tinnitus results from abnormal spontaneous activity somewhere in the auditory pathway, and the neural events that lead to tinnitus are themselves a result of altered activity in the cochlea.[10, 11] Cochlear NMDA receptors have been implicated in neural-generated tinnitus.[10, 12, 13] Acute excitotoxic tinnitus results from administration of salicylate, but prior administration of NMDA receptor blockers prevents salicylate-induced tinnitus.[12] Given this proposed mechanism of action, nitrous oxide, an NMDA receptor antagonist, presents a possible therapeutic strategy for treating tinnitus.

In this pilot study, we plan to assess the impact of nitrous oxide on tinnitus symptoms and degree of bother. For this pilot study, we will not exclude patients with depression, and thus we will not be able to assess whether the mechanism of nitrous oxide on reducing tinnitus is independent of the aforementioned mechanism in depression. Regardless, we believe nitrous oxide may be an effective treatment for tinnitus and believe a pilot study is indicated.

3. DRUG INFORMATION

Nitrous oxide (laughing gas) is a colorless, odorless gas. Nitrous oxide is the oldest and most widely used FDA-approved anesthetic gas. It is commonly used as a component of general

anesthesia and as a sedative/analgesic agent used in hospitals and dentist offices. The onset as well as offset of effect is within a few minutes. Nitrous oxide is the least potent of inhalational anesthetics. Concentrations above 1atm are theoretically needed to produce complete general anesthesia when nitrous oxide is used as a sole agent. Therefore, concentrations typically used (50%) in dentistry and pediatrics achieve only mild to moderate sedation (but potent analgesia) and are not sufficient to produce general anesthesia. Well-known side effects include euphoria, sedation, nausea and vomiting, and inactivation of vitamin B12 (commensurate with the duration of exposure and concentration used). In general, exposure to 50% nitrous oxide for 40 minutes is considered extremely safe. The use of nitrous oxide to treat tinnitus is off-label and outside of the approved indication.

4. ELIGIBILITY

Inclusion Criteria

- a) Adult men and women 18-65 years of age
- b) Subjective, unilateral or bilateral, non pulsatile tinnitus for at least 6 months duration
- c) Either “Bothered more than a little but not a lot”, “Bothered a lot”, or “Extremely bothered” on the Global Bothersome scale
- d) Able to give informed consent
- e) Must be able to read, write, and understand English

Exclusion Criteria

- a) History of:
 - a. Bipolar disorder
 - b. Schizophrenia
 - c. Schizoaffective disorder
 - d. Substance abuse or dependence (except for remote substance abuse or dependence with remission at least 1 year prior to the study and except for nicotine use disorders)
- b) Acute medical illness that may pose subject at risk during nitrous oxide administration
- c) Active psychotic symptoms
- d) Patients with significant pulmonary disease and/or requiring supplemental oxygen
- e) Contraindication against the use of nitrous oxide, including:
 - a. Pneumothorax
 - b. Bowel obstruction
 - c. Middle ear occlusion
 - d. Elevated intracranial pressure
 - e. Chronic cobalamin and/or folate deficiency treated with folic acid or vitamin B12

- f. Pregnancy
- g. Breastfeeding women
- f) Previous NMDA-receptor antagonist treatment (e.g., ketamine) within the last 3 months
- g) Tinnitus related to cochlear implantation, retrocochlear lesion, Meniere's Disease, or other known anatomic lesions of the ear or temporal bone
- h) Tinnitus related to a Workman's Compensation claim or litigation-related event that is still pending.
- i) Any medical condition, which, in the opinion of the PI, confounds study results or places the subject at greater risk

5. SCREENING AND ENROLLMENT

Participants will be recruited from Washington University School of Medicine Department of Otolaryngology-Head and Neck Surgery clinics, including the Division of Audiology. The Washington University Volunteers for Health Research Participant Registry and Otolaryngology Research Participant Registry will be queried to identify potential participants. Potential participants will be screened according to inclusion and exclusion criteria over the telephone, and those who meet inclusion criteria will be invited to the 8th floor McMillan Building Clinical Research Outcomes Office to discuss study participation. The potential participant will have the opportunity to review the consent form and have questions about the study answered by the study team. The PI, or designee, will obtain written consent prior to the start of study related procedures.

We will enroll a total of 40 participants with bothersome tinnitus to achieve at least 30 evaluable participants. Participants will be offered \$50 in remuneration for their time and effort in this study, to be given upon completion of study participation.

6. METHODS

Study Design

This is a prospective, randomized, double-blinded, placebo-controlled crossover trial where 40 patients will undergo two treatment sessions in randomized order. In one session, subjects will receive up to 50% nitrous oxide/50% oxygen for 40 minutes ("Treatment"). In the other session, subjects will receive up to 50% nitrogen [inert]/50% oxygen for 40 minutes ("Placebo"). The two sessions will be held 2 weeks apart and will be indistinguishable from each other in setting, setup, and monitoring.

No pre-enrollment laboratory assessments will be required. However, a health history will be taken at screening.

Randomization

Each participant will be randomly assigned to either the “Treatment first” or “Placebo first” group. The randomization scheme will use permuted blocks of randomly varying sizes generated by the study statistician using SAS statistical software and a password-protected Microsoft Excel spreadsheet will be used to create and store the study IDs and the randomization order. Each block will contain equal numbers of assignments to the treatment first and placebo first in randomized order. To account for the anticipated 20% dropout rate (i.e., as a result of withdrawal, being lost to follow-up, and so on), the randomization table will be generated for 50 subjects.

Blinding

Participants will be blinded to the randomization order. Nitrous oxide is a colorless and odorless gas, which makes it unlikely for participants to identify the group assignment. Likewise, the study setup will be identical for both sessions, which will make an inadvertent unblinding of the study unlikely. For the anesthesiology team responsible for the administration of the nitrous oxide treatment, the group assignment will be known. This team is completely separate from the team assessing the study outcomes, which will be blinded to the treatment received. Treatment administration and outcomes assessment will also be physically separated in different rooms within the Clinical Research Unit (CRU) to prevent unblinding. To assess the integrity of the blind, subjects will be asked immediately after each administration to guess which treatment – active or placebo they just received.

Setting

The study will be performed in the Clinical Research Unit (CRU) at the Center for Applied Research Sciences, located on the 4th and 5th floors of Barnard Hospital. The CRU is staffed by nurses, technicians, and medical assistants with experience in implementing clinical research studies, including specialized protocol-required procedures. The facility consists of 6 rooms and 12 semi-private beds, and is equipped with state-of-the art anesthesia machines, monitoring and anesthesia equipment, and resuscitation equipment and devices. The CRU has anesthesia equipment set up to allow for treatment of two participants at once. We will pay the CRU an annual fee of \$500 for this active protocol.

Administration of Study Treatment

Except for the choice of gas (nitrous oxide or nitrogen [inert]; both mixed with 50% oxygen), treatment sessions will be identical. The gas mix will be administered via a standard anesthesia face mask through tubing connected to the inhalation apparatus. Inhaled and exhaled gas concentrations of nitrous oxide, oxygen and nitrogen will be monitored and adjusted according to protocol. Total gas flow will be 2-4 L/min.

Participants will be NPO (although liquids may be freely consumed) for 2 hours prior to each intervention session as a precaution for possible nausea. Participants will be monitored during and after the treatment according to American Society of Anesthesiologists (ASA) standard, which includes continuous 3-lead ECG, pulse oximetry, non-invasive blood pressure and end tidal CO₂ under the supervision of an attending-level anesthesiologists.[15] After the 40 minute treatment session, participants will be monitored in the CRU for 1 hour. Participants will then be asked to complete the Momentary Assessment of Tinnitus (MAT) questionnaire before leaving. A study team physician will determine when the participant meets criteria for discharge as described by the ASA standard.

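### Does a 50-line randomization table contradict a planned enrolment of 40?

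*Combined protocol and SAP*

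**What the plan says.** The synopsis gives the size without comment: "Number of Patients 40". Section 5 (Screening and Enrollment) supplies the purpose: "We will enroll a total of 40 participants with bothersome tinnitus to achieve at least 30 evaluable participants". In Section 6, Study Design describes a "crossover trial where 40 patients will undergo two treatment sessions in randomized order". Randomization, in the same section, sets up permuted blocks of varying size, balanced between the two orders, and sizes the list. It begins "To account for the anticipated 20% dropout rate", names withdrawal and loss to follow-up as examples, and concludes that "the randomization table will be generated for 50 subjects".

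The protocol does not say whether dropouts are replaced, gives no maximum number randomized, and does not define evaluable. It contains no power calculation, so these counts are its only statement of size.

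**The concern.** Loss appears to be allowed for twice, from different starting points. In Section 5, 40 is the number going in and 30 is the minimum coming out. In Section 6, 50 is what results from dividing 40 by 0.80, so 40 looks like the number coming out.

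The stated reason for the longer table adds to the difficulty. Someone who withdraws or is lost after randomization has already used a line. Dropout of that kind needs further lines only if the person is replaced, and each replacement beyond the fortieth entrant would exceed the Section 5 total. The Study Design sentence, read literally, also has 40 people receiving both sessions, which 40 entrants with 20% loss would not provide.

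If the conflict were a working one, two things would be unclear: whether recruitment stops at 40 or can run to 50, and whether to expect about 32 or about 40 people with data from both sessions.

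**Working it through.** **Inputs.** Enrolment of 40 (synopsis, Section 5); floor of 30 evaluable (Section 5); 20% dropout and a 50-line table (Section 6, Randomization).

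**Reproducing the table length.** n/(1 − d) = 40/(1 − 0.20) = 50 exactly. Multiplying instead, 40 × 1.20 = 48, does not match. So 50 was most likely obtained by inflating 40.

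**Checking Section 5 on its own terms.**
- Expected remaining from 40: 40 × 0.80 = 32, above 30.
- Loss that 40 can absorb before falling below 30: 1 − 30/40 = 25%, above the anticipated 20%.
- Entrants needed for 30 in expectation: 30/0.80 = 37.5, so 38.

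Section 5 is consistent with the 20% figure and does not need the 50.

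**How secure the floor is.** This needs two assumptions that the protocol does not state: dropouts are independent, and evaluable means both sessions completed. The number remaining is then binomial with parameters N and 1 − d. The 15% and 25% rows are an illustrative range.

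| Dropout | P(at least 30), N = 40 | P(at least 30), N = 50 |
|---|---|---|
| 15% | 0.970 | above 0.999 |
| 20% | 0.839 | 0.9997 |
| 25% | 0.584 | 0.994 |

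**What the two readings mean for precision.** Take a simple paired comparison as a rough stand-in for the planned mixed model. The 95% half-width in units of the SD of the paired difference is t(0.975, n − 1)/√n:
- n = 32: 0.361
- n = 40: 0.320
- difference: 0.361 − 0.320 = 0.041 SD

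**Setting the statements side by side.** The synopsis and Section 5 both give 40, and only Section 5 mentions loss. The Randomization paragraph gives the length of a list; it does not say that 50 people will be enrolled or that 40 will remain. The Study Design sentence describes what a crossover does and makes no statement about completion. One reading fits all four statements: enrol 40, assign from a list with ten spare lines, and accept some loss down to 30.

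**The case for a change.** The strongest reply is that the spare lines are not offered as a general reserve. The protocol gives a reason, and that reason is loss after assignment. On that reason the lines have a use only if dropouts are replaced, so either the reason is misplaced or the total of 40 is not a true ceiling. Reading enrolment as consent, with randomization later, does not help, because at most 40 would then be randomized. With no power calculation, these counts carry more weight than usual, and an unwritten replacement rule could leave a decision to go past 40 to be taken during the trial. Entry to the second session also depends on the bother score being within one category of baseline (Section 7), which could add incomplete pairs.

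Most of this stands as a description of the text: the reason does not fit a fixed total of 40, and the replacement rule is absent. It does not show that following the plan goes wrong. That 40 means the number left after dropout is an inference from an exact division, and nothing in the text says it. The synopsis fits either reading. The enrolment statement in Section 5 is explicit, and a list with unused lines does no harm. Nor does a dropout after the first session necessarily leave the primary analysis, since the Section 9 mixed model can use the measures that are available; it is McNemar's test that needs both sessions.

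**Conclusion.** The concern does not call for a change. The 50-line table is best read as a list with slack and a loosely worded reason. Enrolling 40 as Section 5 directs gives 32 expected against a floor of 30 at the protocol's own 20% dropout, and no stated power or precision target is missed. If people were replaced up to 50, the floor would be met more comfortably still.

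The residual uncertainty is limited. It is 40 or 50 as the most that could be randomized, about 32 or 40 expected with both sessions, and roughly 0.04 SD in half-width. With 40 enrolled, the chance of falling short of 30 is about 1 − 0.84 = 16%. That figure rests on independent dropout at 20% and on equating evaluable with both sessions completed, and it moves to 3% at 15% dropout and 42% at 25%. A shortfall would make a pilot estimate somewhat less precise; it would not bias the comparison.

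Rewording would leave the design and the analysis as they are, and the only substantive alternative is to recruit up to ten more people for a target the plan already expects to meet. Whether dropouts are replaced, and what evaluable means, are points the study team can settle in its working documents and report with the participant flow.

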7. DATA COLLECTION

Assessment of Treatment Efficacy

Baseline and Treatment Efficacy Assessment Forms:

1. Demographics
2. Tinnitus Description and History Form
3. Global Bothersome Scale (GBS)
4. Tinnitus Functional Index (TFI)
5. Momentary Assessment of Tinnitus Questionnaire (MAT)
6. Patient Health Questionnaire (PHQ-9)
7. Patients' Global Impression of Change (PGIC)

The effects of the treatment will be assessed using repeat administration of GBS, TFI, MAT, PHQ-9, and PGIC.

Participants will be asked to complete forms 1-6 (detailed above) immediately before each of two sessions as **baseline assessment**, with Demographics and Tinnitus Description and History Form only required before the first session. One hour and then one day following each intervention, participants will complete EMA. One week following each session, participants will complete GBS, TFI, MAT, PHQ-9, and PGIC. These constitute the **treatment efficacy assessment**. In total, each participant will complete the baseline assessment at two timepoints and treatment efficacy assessment at 6 timepoints. The two sessions will be 14 days (2 weeks)

apart. These questionnaires can be completed online via a link provided through REDCap in an email to the participant. At 14 days after administration of nitrous oxide, we expect the effects of nitrous oxide to wear off fully and patients' tinnitus should have returned to baseline. The baseline assessment for the second session will take place no sooner than 14 days after the first session, and therefore will assess whether this washout period of 14 days is accurate. The patient will not be allowed to participate in the second arm of the study until their Global Bother Scale score is within one category of their baseline score.

Assessment of Treatment Safety

Treatment safety will be assessed at several levels: adverse events (AE) related to (i) cardiovascular status; (ii) respiratory function; (iii) central nervous system; (iv) psychiatric symptoms,.

- (i) Cardiovascular AEs, such as hyper- and hypotension, tachy-/bradycardia, will be identified by continuous hemodynamic monitoring during and after the treatment
- (ii) Respiratory AEs, such as respiratory depression and desaturation, will be identified by continuous pulse oximetry during and after treatment
- (iii) Central nervous system AEs will be assessed clinically.
- (iv) Psychiatric AEs, will be assessed clinically.

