10. RISK ASSESSMENT

Nitrous oxide. The side effects of nitrous oxide are well known to anesthesiologists. The dose (50%) and duration (40 minutes) used in this protocol are considered extremely safe and of low risk. Similar doses and durations are used in everyday dental practice without vital sign monitoring or supervision by a resuscitation-trained physician. With this dose of nitrous oxide, sedation may occur but not general anesthesia or respiratory depression. Previous evidence shows that the inactivating effect of nitrous oxide on vitamin B12 is dose and duration-dependent and are minor when used as described in this protocol. An increase in plasma homocysteine by +25% and return to baseline within the next 24 hours is expected. Minor side effects after nitrous oxide exposure such as nausea and vomiting may occur which are typically self-limited and short. As a precaution against nausea, patients will be NPO for 2 hours prior to each intervention session, although liquids may be freely consumed. If a patient develops moderate to severe nausea and vomiting, we will administer 4mg of ondansetron.

Questionnaires. Participants may experience frustration and/or boredom completing the questionnaires. The participants may refuse to answer any questions for any reason.

REFERENCES

2. Lechtenberg, Richard, and Abraham Shulman. "Benzodiazepines in the treatment of tinnitus." *The Journal of Laryngology & Otology* 98.S9 (1984): 271-276.
3. Lockwood, Alan H., Richard J. Salvi, and Robert F. Burkard. "Tinnitus." *New England Journal of Medicine* 347.12 (2002): 904-910.
4. Langguth, Berthold, Richard Salvi, and Ana Belén Elgoyhen. "Emerging pharmacotherapy of tinnitus." *Expert opinion on emerging drugs* 14.4 (2009): 687-702.
5. Langguth, Berthold, and Ana Belén Elgoyhen. "Current pharmacological treatments for tinnitus." *Expert opinion on pharmacotherapy* 13.17 (2012): 2495-2509.
6. Beebe Palumbo, Devon, et al. "The Management and Outcomes of Pharmacological Treatments for Tinnitus." *Current neuropharmacology* 13.5 (2015): 692-700.
7. Drug Therapies, American Tinnitus Association <https://www.ata.org/managing-your-tinnitus/treatment-options/drug-therapies>.

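### Does the blinding rationale, silent on sedation and with no stated summary of the treatment guesses, require a change to the plan?

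*Combined protocol and SAP*

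**What the plan says.** Section 6 (Blinding) first states the aim: "Participants will be blinded to the randomization order". It gives two reasons why participants should not recognise the gas: its lack of colour and smell ("Nitrous oxide is a colorless and odorless gas, which makes it unlikely for participants to identify the group assignment") and an identical setup at both sessions. It then says that the anesthesiology team knows the assignment, and adds: "This team is completely separate from the team assessing the study outcomes, which will be blinded to the treatment received". Administration and outcome assessment take place in different rooms. Finally it provides a check: "To assess the integrity of the blind, subjects will be asked immediately after each administration to guess which treatment", with active and placebo as the choices.

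Section 3 (Drug Information) says that "concentrations typically used (50%) in dentistry and pediatrics achieve only mild to moderate sedation" and lists euphoria and nausea among the known side effects. Section 10 (Risk Assessment) says "With this dose of nitrous oxide, sedation may occur but not general anesthesia or respiratory depression". The comparator is inert nitrogen with oxygen.

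Section 7 (Data Collection) states "One week following each session, participants will complete GBS, TFI, MAT, PHQ-9, and PGIC" and "These questionnaires can be completed online via a link provided through REDCap in an email to the participant". The guess is not among the seven listed forms.

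Section 9 (Data Analysis) provides general descriptive statistics, a mixed model for TFI with measures nested within subjects, a look at carry-over, and McNemar's test for a TFI difference of 13 points or more. It mentions neither the guesses nor the blind.

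**The concern.** The reasons given for participant blinding cover what can be seen and smelled, but not what can be felt. A sedating gas is compared with an inert one, and every participant receives both, so each can compare the two experiences directly. The outcome is patient-reported, so a participant who recognises the gas may score the TFI differently because of that belief. A separate outcomes team cannot prevent this.

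The guesses are then the reader's main evidence on how far a TFI difference could reflect expectation, and their summary is not specified. If participants know that they receive each gas once, the second guess will tend to be the opposite of the first. A plain table by gas, tested as two independent groups, would then overstate the evidence of unblinding. The same data could be read as a broken blind or as inconclusive, depending on a choice made after the TFI result is known.

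**Working it through.** The protocol states no figure for blinding or for the guesses, so there is none to reproduce. Two checks apply: what the texts say side by side, and how much the choice of summary could matter.

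**Texts side by side**

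- Section 6 calls recognition unlikely. Sections 3 and 10 say that sedation is achieved or may occur at 50%. Both can hold, so the rationale is incomplete rather than contradicted.
- Section 6 brings in the separate team straight after saying that the anesthesiology team is unblinded. It answers leakage from staff. It is not offered as protection against recognition by the participant, so self-completion of the TFI does not conflict with it.
- The guess after each session shows that the plan allows for recognition.

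**Effect of ignoring the pairing**

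Inputs: n = 30 (the minimum evaluable number in Section 5), giving 60 guesses. Assumptions: an intact blind, and a probability of 0.5 of guessing active with each gas. The correlation between a participant's two guesses is not given and is varied.

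Let g1 and g0 be the proportions guessing active after nitrous oxide and after placebo. With common rate p and correlation r between the two guesses,

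var(g1 − g0) = 2p(1 − p)(1 − r)/n.

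An unpaired test sets r = 0. If r is negative it understates the variance; if r is positive it overstates it.

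*Always-opposite guesses (r = −1).* Let b participants be right in both sessions and 30 − b wrong in both.

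- Unpaired: the standard error is √(2 × 0.25/30) = 0.1291, so |z| > 1.96 needs |2b − 30| > 1.96 × 0.1291 × 30 = 7.59. That means b ≥ 19 or b ≤ 11. Under Binomial(30, 0.5) the probability is 0.2005.
- Paired adjusted Wald 95% interval (0.5 added to each of the four cells): it excludes zero when b ≥ 21 or b ≤ 9. The probability is 2 × 0.0214 = 0.0428.

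*Other correlations.* These come from exact enumeration of the four guess-pair cells, with an assumed bivariate normal model behind the guesses:

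| Latent correlation | Unpaired test flags | Paired interval excludes zero |
|---|---|---|
| always opposite | 20.0% | 4.3% |
| −0.9 | 13.9% | 6.0% |
| −0.5 | 9.3% | 5.3% |
| 0 | 5.2% | 5.5% |
| +0.3 | 3.0% | 5.3% |

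*One data set, two readings.* Let b = 19, so 19/30 (63%) guess active after nitrous oxide and 11/30 (37%) after placebo.

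- Unpaired: z = (8/30)/0.1291 = 2.07, p = 0.039.
- Exact McNemar, 19 against 11: p = 0.20.
- Paired interval: the difference is (19.5 − 11.5)/32 = 0.25 and the standard error is √(31 − 8²/32)/32 = 0.168. The interval is 0.25 ± 1.96 × 0.168, or −0.08 to 0.58.

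**Does the plan call for the unpaired test?** No. The guesses are binary outcomes measured twice in each person. For the other outcome of that form, the 13-point TFI responder, Section 9 names McNemar's test. Applied to the guesses, the same test gives the second reading above.

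**The case for a change.** The strongest case for a change is that it would be cheap and the stakes are real. The stated objective is efficacy, the primary outcome is self-reported, and the only evidence on the participants' blind has no stated summary. A few sentences would acknowledge the felt effects, fix a paired summary before the TFI result is known, and warn that an interval including zero does not prove that the blind held. If the guesses are uncorrelated, pairing costs nothing.

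Much of this stands. The omission in Section 6 is real, Section 9 is silent on the guesses, and the arithmetic is right. A careful report would show guesses by gas and period, show first-session guesses separately because they cannot be deduced from an earlier guess, and pair any comparison between gases.

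It does not follow that the plan must change. The 20.0% figure measures an error that the plan does not propose. It also needs every participant to give opposite guesses, which rests on what participants are told about receiving each gas once; that text is not available here. At positive correlation the unpaired test errs the other way. The check is also weak whatever is written down: with opposite guesses and true rates of 0.60 and 0.40, the paired interval detects the difference only 17.6% of the time.

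**Conclusion.** No change to the plan is needed. The rationale in Section 6 is incomplete and the summary of the guesses is unstated, but no stated rule gives a wrong result. The guesses are collected at both sessions, sedation is disclosed in Sections 3 and 10, and the TFI estimate and its test are the same with or without added wording. What is missing is detail that a statistician who already specifies McNemar's test and a within-subject model can be expected to supply.

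If the pairing were nevertheless ignored, the false-flag rate for the blinding check would lie between 3.0% and 20.0% over the correlations examined, at n = 30 and guess rates of 0.5. Only the secondary reading of the blind would be affected. The protocol gives no guess rates and no expectation effect, so the size of any bias in the TFI from unblinding cannot be computed. This conclusion assumes that the guesses will be reported and kept linked within participant, which the plan does not state but its other analyses make likely.
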